## 7.2 General Methodology

All data collected from the time of screening until the end of the study will be collected either on eCRFs, subject questionnaires or electronically by downloading the various devices. Data and analysis will be summarized in a Clinical Study Report. For China, the Clinical Study Report will be compliant with NMPA 2016 No. 58 Announcement Annex 5 "Template of Clinical Trial Report of Medical Devices".

Any deviations from original statistical plan and the rationale will be described in the Clinical Study Report.

There will be no interim analysis perform during the study so therefore there are no criteria and/ reasons for trial termination based on statistics.

## 7.3 Center Pooling

Data will be pooled for analysis.

## 7.4 Handling of Missing, Unused, and Spurious Data and Dropouts

Data entry error or non-reasonable values will be resolved before data analysis. No imputation will be applied for the device data.

## 7.5 Adjustments for Multiple Comparisons

Not Applicable.

## 7.6 Demographic and Other Baseline Characteristics

Subject characteristics, including age, gender, race, ethnicity, length of type 1 diabetes diagnosis, height, weight, BMI, and baseline HbA1c will be summarized by descriptive statistics (mean, standard deviation, minimum, median, and maximum) for continuous variables and by counts and percentages for categorical variables.

## 7.7 Treatment Characteristics

Not Applicable.

## 7.8 Interim Analyses

Not Applicable.

## 7.9 Evaluation of Objectives

### 7.9.1 Primary Endpoints

Time in target range (% of SG): 70 mg/dL (3.9 mmol/L) ≤ SG ≤ 180 mg/dL (10 mmol/L)

The overall mean change in % of time in target range from run-in period to study period will be estimated and compared by a simple superiority paired test and a significance level of 0.025 (one-sided).

$H_0: \mu \leq 0\%$

$H_a: \mu > 0\%$

Where  $\mu$  is the mean of change in % of time in target range (1-month - baseline). The null hypothesis will be rejected if the one-sided 97.5% lower confidence limit of the mean change in % of time in target range is greater than 0%.

- Pass/Fail Criteria

The study pass/fail criteria is based on statistical hypothesis of the primary endpoint. The study will be considered as success when the evaluation criteria meets the predefined threshold.

- Justification for Exclusion of Particular Information from the testing of the Hypothesis

Not Applicable.

### 7.9.2 Secondary Endpoints

- Time in hypoglycemic range (% of SG): SG < 70 mg/dL (3.9 mmol/L), 60 mg/dL (3.3 mmol/L) and 54 mg/dL (3.0 mmol/L)
- Time in hyperglycemic range: SG > 180 mg/dL (10 mmol/L), 250 mg/dL (13.9 mmol/L) and 350 mg/dL (19.4 mmol/L)
- Glucose variation: the standard deviation (SD) of SG and the glucose coefficient of variation (CV)
- Change of Total Daily Dose (TDD) of insulin and weight from baseline to EOS

- Time spent in Auto Mode (HCL) versus time spent in Manual Mode (open loop)
- Stratified by HbA1c Ranges (< 7%, 7 – 7.5%, 7.5 – 8%, > 8%)
  - Time in target range (% of SG): 70 mg/dL (3.9 mmol/L) ≤ SG ≤ 180 mg/dL (10 mmol/L)
  - Time in hypoglycemic range (% of SG): SG < 70 mg/dL (3.9 mmol/L), 60 mg/dL (3.3 mmol/L) and 54 mg/dL (3.0 mmol/L)
  - Time in hyperglycemic range: SG > 180 mg/dL (10 mmol/L), 250 mg/dL (13.9 mmol/L) and 350 mg/dL (19.4 mmol/L)

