#### *Study-specific inclusion criteria*

3. Subject is willing to perform  $\geq$  4 finger stick BG measurements daily.
4. Subject is willing to perform required sensor calibrations.
5. Subject is willing to wear the system continuously throughout the study.
6. Subject must have a minimum daily insulin requirement (Total Daily Dose) of greater than or equal to 8 units.
7. Subject has a Glycosylated hemoglobin (HbA1c) less than 10% (as processed by the investigational center lab or their contracted Local Lab) at time of Screening visit.
8. Subject has thyroid-stimulating hormone (TSH) in the normal range OR if the TSH is out of normal reference range the Free T3 is below or within the lab's reference range and Free T4 is within the normal reference range. Prior labs in the last 6 months are sufficient.
9. Subject has been on pump therapy for greater than 6 months prior to screening (with or without CGM experience).
10. Subject is willing to upload data from the study pump and meter at home.
11. If subject has celiac disease, it has been adequately treated as determined by the investigator.
12. Subject has been taking and is willing to take one of the following insulins throughout the course of the study:
  - o Humalog™\* (insulin lispro injection)
  - o NovoLog™\* (insulin aspart)
13. Subject must be able to carbohydrate count or willing to learn how to carbohydrate count for the study.

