### 9.7.3. HbA1c

Collected at screening for exclusion criteria.

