## **5. Investigation Plan**

This study is a multi-center, single arm study in insulin-requiring subjects with type 1 diabetes who are 14 years of age and older. The run-in period will be approximately up to 35 days long, followed by a study period that will be approximately up to 33 days in duration.

The study is anticipated to last no longer than 13 months from investigational center initiation to completion of all data entry and monitoring procedures. The study will target approximately 5 months to complete subject enrollment. Subjects can expect to participate for approximately 2-3 months including the run-in and study periods.

A total of up to 75 subjects (aged 14-75) will be enrolled at a minimum 2 investigational centers and up to 6 investigational centers (hospitals) in China to have at least 50 subjects who complete the study.

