## **6. Determination of Sample Size**

Based on US pivotal study outcome, the estimated difference of the TIR from run-in period to study period to be expected 5.3%. A sample size of 50 will achieve greater than 80% power to detect simple superiority using a one-sided t-test with a standard deviation of 13.0% at the significance level (alpha) of 0.025.

This study will enroll subjects between age of 14 and 75 years old, with an expected ratio (1:5) between Adolescents (14-17 years) and Adults ( $\geq 18$  years) to complete the study.

A total of up to 75 subjects will be enrolled at minimum 2 investigational centers and up to 6 investigational centers (hospitals) in China considering potential drop outs. A maximum of 30 subjects will be enrolled at each investigational center. Sites with less than 6 subjects will be pooled into 'pseudo-sites' of at least 10 subjects per pseudo-site. Pseudo-sites will be pooled by ranking those sites with less than 6 subjects by site number and pooling those sites in order of site number until the number of subjects reaches at least 10.

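### Do the HbA1c strata, which share the bound 7.5%, lead to subjects being counted twice?

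*SAP*

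**What the plan says.** SAP section 7.9.2 lists time in target range, time in hypoglycemic range (three thresholds) and time in hyperglycemic range (three thresholds) a second time, now "Stratified by HbA1c Ranges (< 7%, 7 – 7.5%, 7.5 – 8%, > 8" per cent. The protocol prints the same four ranges in the synopsis (section 3) and in sections 5.2.2 and 14.6.2.

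The only HbA1c value that can define the strata is the screening value. Protocol section 9.7.3 describes HbA1c as "Collected at screening for exclusion criteria", and the visit list in section 9.1 has it at Visit 1 only. The eligibility limit in section 8.3 is "Subject has a Glycosylated hemoglobin (HbA1c) less than 10" per cent, so 7.5% lies well inside the eligible range.

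Success is defined elsewhere. SAP section 7.9.1 states that "The study pass/fail criteria is based on statistical hypothesis of the primary endpoint". No hypothesis, test or threshold is attached to the HbA1c strata in either document.

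**The concern.** The two outer ranges are strict: below 7 and above 8. The values 7.0% and 8.0% are therefore covered only if the middle ranges include their end points. If both middle ranges are closed, 7.5% belongs to both. If both are open, 7.0%, 7.5% and 8.0% belong to none. No uniform reading of the dashes gives a clean partition.

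Read literally as closed ranges, the rule makes the stratum counts add up to more than the analysis total, and two neighbouring strata share subjects. If an analyst instead has to pick a side, the choice is made without a written rule in an open-label, single-arm study whose results go to a regulator. The middle strata are small, so a few subjects could move their means. That is why the point deserves a check.

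**Working it through.** **1. The plan's own figure, and whether the strata enter it.** SAP section 6 takes a mean change in time in range of 5.3 percentage points, an SD of 13.0 and a one-sided alpha of 0.025, and states: "A sample size of 50 will achieve greater than 80% power to detect simple superiority using a one-sided t-test". The noncentrality parameter is 5.3 / (13.0 / √50) = 2.88, and the critical t on 49 degrees of freedom at one-sided 0.025 is 2.01. Power from the noncentral t distribution is 80.7%, so the stated figure of more than 80% reproduces. HbA1c appears nowhere in this calculation or in the primary test.

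**2. Which values are ambiguous.** Each HbA1c value from 5.0 to 9.9% in steps of 0.1 was assigned under three readings.

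| Reading of the middle ranges | Values in two strata | Values in no stratum |
|---|---|---|
| Both closed | 7.5 | none |
| Both open | none | 7.0, 7.5, 8.0 |
| 7 to below 7.5; 7.5 to 8 | none | none |

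Only the value 7.5% is ever counted twice, and only under the first reading. Giving 7.5% to one stratum and keeping 7.0% and 8.0% in the middle ranges produces a partition.

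**3. How many subjects.** The documents give no SD for HbA1c in this population and no reporting precision, so these are assumptions: normal distribution, mean m from 7.0 to 8.0%, SD s from 0.8 to 1.0%, reporting to one decimal, truncation below 10%. Then

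p = [Φ((7.55 − m)/s) − Φ((7.45 − m)/s)] / Φ((9.95 − m)/s).

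- Lowest, at m = 7.0 and s = 1.0: [Φ(0.55) − Φ(0.45)] / Φ(2.95) = 0.035.
- Highest, at m = 7.5 and s = 0.8: [Φ(0.0625) − Φ(−0.0625)] / Φ(3.0625) = 0.050.
- Expected number among 50: 50p = 1.8 to 2.5.
- Chance of at least one among 50: 1 − (1 − p)^50 = 83 to 92%.

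With the SD widened to 0.7 to 1.2%, p is roughly 3 to 5.7% and the chance of at least one is 79 to 95%. With two-decimal reporting, p falls about tenfold, to 0.35 to 0.50%, or about 0.2 subjects in 50.

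**4. What one or two subjects can do to a stratum.** Under the assumptions of step 3, a closed middle stratum holds about 9 to 15 of 50 subjects, and those at 7.5% make up about 15 to 21% of it. Take 12 subjects with 2 at the boundary. Suppose the change in time in range has the planning SD of 13.0 within the stratum and the boundary subjects resemble the rest. Leaving the 2 out then shifts the stratum mean by a random amount with SD 13.0 × √(1/10 − 1/12) = 1.7 points. The standard error of that mean is 13.0 / √12 = 3.8 points with them and 13.0 / √10 = 4.1 points without. The shift is less than half the sampling error already present.

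**The case for a change.** The strongest argument for acting is that the defect is printed four times across two documents, will probably touch at least one subject, and could be removed with one line of wording. Elsewhere the authors write bounds exactly, as in the definition of the target range. SAP section 8 allows validation by independent programming. Two programmers might place 7.5% differently, and the SAP could not say who is right.

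Part of this stands. The boundary is unspecified, and this is not an artefact of reading the PDF. The rest carries little weight:

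- Neither document instructs double counting, and a programmer building a four-level variable will give each subject one level.
- Even with double counting, a subject appears once within any one stratum's summary. The visible effect would be stratum counts that exceed the total, which either form of validation in SAP section 8 has a fair chance of catching. A mismatch between two programmers would likewise show up and be settled.
- A choice of side made after seeing open-label data could gain little, because no decision depends on these summaries and the shift is within sampling error.
- Neither placement is better than the other, so a written rule would add tidiness but not validity.
- The wording also sits in the protocol. Under protocol section 16.8, even an administrative amendment goes to the ethics committees for notification and is signed by the investigators. That is more than one line of effort for no change in what the trial can conclude.

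**Conclusion.** The ranges share the bound 7.5% and the plan leaves that value unassigned. This is missing detail in a set of descriptive breakdowns. It does not instruct anyone to count subjects twice. On assumed one-decimal reporting, mean 7.0 to 8.0% and SD 0.8 to 1.0%, about 2 of 50 subjects are concerned. With two-decimal reporting it would probably be none.

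Placing them in either middle stratum is defensible, and for a stratum of 12 the choice typically moves its mean by about 1.7 points against a standard error of about 4. The primary test, the power of 80.7%, the pass/fail rule and all unstratified secondary endpoints are the same whichever way 7.5% is assigned. The programmer can settle the point when deriving the variable and note the choice in the table footnote. No change to the plan is needed.

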### **7.9.3 Safety**

All adverse events will be collected from enrollment (i.e., time of consent) to study end including but not limited to:

- Serious Adverse Events (SAE)
- Serious Adverse Device Events (SADE)
- Unanticipated Adverse Device Effects (UADE)
- Incidence of Severe Hypoglycemia
- Incidence of Severe Hyperglycemia
- Incidence of DKA

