##### **3.1.2 Current Evidence of Clinical Benefits**

Previous studies have shown that the MiniMed™ 670G system can increase time in target glucose range, reduce time spent in the hyperglycemic range without increasing the risk of hypoglycemia, and improve overall glycemic control in individuals with T1DM. The pivotal clinical trial, which directly results in the United States Food and Drug Administration's (FDA) approval on September 28, 2016, investigated the safety of MiniMed™ 670G system and the effects of HCL Auto Mode on glycemic control in 124 patients (ages 14-75 years) with T1DM from 10 hospitals in the United States or Israel. In the CEP294 trial, the study participants had a 2-week run-in period to learn the devices with HCL Auto Mode off followed by a 3-month study period with HCL Auto Mode on.

The trial results have shown that over 12,389 patient-days, no episodes of severe hypoglycemia or ketoacidosis were observed and 28 device-related adverse events (AEs) that were resolved at home [Bergenstal et al, 2016]. The trial has also demonstrated improved glucose outcomes from the HCL Auto Mode [Garg et al 2017]. From baseline run-in to the end of study phase, both adolescent and adult HbA1c levels decreased significantly from 7.7% to 7.1% and from 7.3% to 6.7%, respectively (both  $P < 0.001$ ). The proportion of overall in-target (71–180 mg/dL) sensor glucose (SG) values increased from 60.4% to 67.2% ( $P < 0.001$ ) in adolescents and from 68.8% to 73.8% ( $P < 0.001$ ) in adults. The SG values in hyperglycemic ( $> 180$ mg/dL) and hypoglycemic ( $\leq 70$ mg/dL) ranges reduced significantly in both adolescents and adults. In particular, nighttime SG values in the hypoglycemic range ( $\leq 70$ mg/dL)

reduced from 5.8% to 2.9% in adolescents and from 6.6% to 3.2% in adults. The variability of SG values during HCL Auto Mode decreased significantly compared with those at baseline.

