### **4.1.1 Primary Objective(s)**

To evaluate the safety, effectiveness and usability of the Medtronic MiniMed™ 670G system in Chinese patients with type 1 diabetes.

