#### **7.1.3 Analysis Sets**

- Intention to Treat (ITT) Population  
The Intention to Treat (ITT) population will include all subjects who start the study period.
- Per Protocol (PP) Population  
The Per Protocol (PP) population will include all subjects who complete the study period and stay in Auto Mode  $\geq 80\%$  of study period and have no major deviations (e.g. protocol violation in eligibility).
- Efficacy Population  
The primary analysis will be performed on the ITT population. Sensitivity analysis will be performed on PP population.
- Safety Population  
The Safety Population will include all enrolled subjects.

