## **7.10 Safety Evaluation**

All adverse events will be collected from enrollment (i.e., time of consent) to study end including but not limited to:

- Serious Adverse Events (SAE)
- Serious Adverse Device Events (SADE)
- Unanticipated Adverse Device Effects (UADE)
- Incidence of Severe Hypoglycemia
- Incidence of Severe Hyperglycemia
- Incidence of DKA

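### Safety is in the primary objective, but severe hypoglycemia and DKA are to be given only as an incidence with no interval, pooled from consent, so a zero count would show no limit on the rate

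*SAP*

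**What the plan says.** The only objective, in SAP 4.1.1 and Protocol 5.1.1, is "To evaluate the safety, effectiveness and usability of the Medtronic MiniMed™ 670G system in Chinese patients with type 1 diabetes".

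SAP 7.9.3 is a list of event types, among them "Incidence of Severe Hypoglycemia". SAP 7.10 repeats the list, including "Incidence of DKA", under the lead-in "All adverse events will be collected from enrollment (i.e., time of consent) to study end including but not limited to". Protocol 5.2.3 and 14.7 do the same. Neither document gives an estimator, an exposure-adjusted rate, a split by period or a confidence interval for any safety result. The only confidence limit in the SAP is the one for time in range in 7.9.1, and study success rests on that endpoint alone.

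On the denominator, SAP 7.1.3 states: "The Safety Population will include all enrolled subjects". Under Protocol 8.2 a subject is enrolled on signing consent. The run-in, of up to 35 days, has Auto Mode off.

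As background, SAP 3.1.2 reports that in the US pivotal trial "over 12,389 patient-days, no episodes of severe hypoglycemia or ketoacidosis were observed".

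**The concern.** A count of zero means little until the reader knows how much exposure lies behind it. This trial is short and small, and the US record suggests that severe hypoglycemia and DKA are uncommon with this system, so a zero is a realistic outcome. Reported bare, it would stand beside a US zero that rests on far more patient-time, and nothing in the tables would show the difference.

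The denominator adds to the problem. All enrolled subjects from consent includes people who never start Auto Mode, and weeks when nobody uses it. A single incidence on that basis describes neither the run-in nor the treatment under evaluation.

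**Working it through.** **The plan's own figure.** The documents state no precision for safety. The one sample-size figure is power above 80% for time in range with n = 50. With a difference of 5.3, SD 13.0 and one-sided alpha 0.025, the noncentrality is 5.3/13.0 × √50 = 2.88 and the paired t-test power is 80.7%, so the claim reproduces. It does not bear on rare events.

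**Inputs**
- Subjects: SAP 5 aims "to have at least 50 subjects who complete the study"; SAP 6 says "A total of up to 75 subjects will be enrolled at minimum 2 investigational centers". The range is therefore 50 to 75.
- Auto Mode time: the last visit is 30 ± 3 days after Visit 4 (Protocol 9.1), so 27 to 33 days.
- Run-in: at least 2 + 0 + 14 = 16 days by the visit windows, at most 35.
- US record: 0 events in 12,389 days = 33.9 patient-years (365.25 days per year).

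**Formulas for zero events.** The exact two-sided 95% upper limit for a rate is −ln(0.025)/T = 3.689/T, with T in patient-years. For a proportion it is 1 − 0.025^(1/N). The chance of no event at rate r is exp(−rT).

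**Upper limits if no event is seen**

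| Exposure | Patient-years | Upper limit per patient-year |
|---|---|---|
| Auto Mode, 50 × 27 days | 3.70 | 1.00 |
| Auto Mode, 50 × 30 days | 4.11 | 0.90 |
| Auto Mode, 75 × 30 days | 6.16 | 0.60 |
| Auto Mode, 75 × 33 days | 6.78 | 0.54 |
| From consent, 50 × (16 + 30) days | 6.3 | 0.59 |
| From consent, 75 × (35 + 33) days | 14.0 | 0.26 |
| US record, 12,389 days | 33.9 | 0.11 |

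By subject, 0/50 gives 7.1% and 0/75 gives 4.8%.

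**How probable is a zero?** At r = 0.109, the US upper limit, the chance of no event on Auto Mode is exp(−0.109 × 4.11) = 64% for 50 × 30 days and 51% for 75 × 30 days. At the extreme of 75 × 33 days it is about 48%. Over the longest window from consent (14.0 patient-years) it is 22%. Lower true rates raise all of these.

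**Comparison with the US record.** 12,389/1,500 = 8.3, so the US limit is about 8 times tighter than that from 50 × 30 Auto Mode days. The ratio is approximate. SAP 3.1.2 does not say whether the US days include that trial's 2-week run-in, and 12,389/124 = 99.9 days per patient is more than three months. If 14 days for each of the 124 patients were run-in (an assumption), 12,389 − 1,736 = 10,653 days remain and the ratio is 7.1.

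**The case against.** Four points on the other side have weight.

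- **Zero is not assured.** A reader might infer that zero is likely even if the true rate were well above what the US data allow. The figures do not support that. With 4.11 patient-years, zero is more likely than not only below ln 2/4.11 = 0.17 per patient-year, about 1.5 times the US limit. At 0.3 per patient-year the chance is 29%.
- **Auto Mode days are not the SAP's window.** As written, events count from consent. On that basis the limits are about 0.59 to 0.26, some 5.4 to 2.4 times the US figure. A reader who takes the exposure to be one eighth of the US total should note that this holds only for 50 × 30 Auto Mode days; at 75 × 33 days it is about one fifth. This stands, and it is a reason to report the periods separately.
- **No document says that safety will be concluded from a zero.** A reader might infer it, but the plan sets no safety criterion and leaves pass/fail to time in range. Nor does the list of events forbid intervals.
- **Other safeguards exist.** There is an external Clinical Events Committee, there are stopping rules, and sensor time below 70, 60 and 54 mg/dL is a secondary endpoint. The first two deal with individual events. Sensor time is not severe hypoglycemia as Protocol 11.2 defines it, and does not address DKA. None of them bounds an incidence.

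It can also be said that any reader could compute the subject-level limit from a count and N. That is true once N is the right one; an all-enrolled N does not give the Auto Mode limit. Finally, since a subject is withdrawn after severe hypoglycemia or DKA, the proportion and the rate will largely agree for those events. The rate is still needed for comparison with a record given in patient-days.

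**Conclusion.** The point holds as a gap in reporting. Safety is part of the primary objective, but the plan attaches no uncertainty to any safety event and pools time with and without Auto Mode.

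If the true rate is at or below 0.11 per patient-year, zero events on Auto Mode is more likely than not for 30-day follow-up of 50 to 75 subjects. That zero would leave rates up to about 0.90 per patient-year unexcluded with 50 × 30 days (1.00 to 0.54 across the planned range), and subject risks up to 7.1% or 4.8%. From consent, the limit is about 0.59 to 0.26.

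These figures assume a constant event rate and full follow-up; the chances of a zero also assume an event rate here similar to the US one. The comparison of about 8 times is approximate for the reason given above. The data, the primary test and the success decision are unaffected, so this is a cheap improvement to what the trial can say about safety and not a flaw in its design.

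**What to change.** In SAP 7.9.3 and 7.10, for severe hypoglycemia, severe hyperglycemia, DKA and SADE:

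- report subjects with an event, number of events and patient-time separately for the run-in and for the study (Auto Mode) period, with subjects who start the study period as the Auto Mode denominator;
- give an exact Clopper-Pearson 95% interval for the proportion and an exact Poisson 95% interval for the rate, including when the count is zero;
- state the upper limit in any conclusion about safety.

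The summary over all enrolled subjects can stay alongside. No hypothesis test, safety criterion or extra subjects are needed. The cost is a few SAP sentences, some table columns and a less flattering safety statement.
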